### STUDY AIMS:

**Aim 1. TR+UC is superior to UC alone:** A 6-week program of TR targeting arm movement added to UC will result in better arm function as compared to UC alone. The primary endpoint is the change in Action Research Arm Test (ARAT) from baseline to 1 month after end of therapy.

**Aim 2. TR+Sinemet is superior to TR+placebo:** Among patients randomized to TR, gains in arm function will be greater in those who take Sinemet (25/100) each day prior to TR, as compared to patients who take placebo each day prior to TR.

**Aim 3. Less CST injury and higher dopamine polygene score predict better recovery of arm function:** Across all subjects, change in arm function will be highest in those with lower % CST injury and in those with higher dopamine polygene scores. These relationships will remain significant when examining only patients randomized to TR. The drug X gene score interaction term will be significant such that the slope of arm gains in relation to the polygene score will be smaller (less steep) in those receiving Sinemet.

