## Randomize the patient

Using a web-based randomization procedure, the patient will be randomized into one of three treatment groups:

- **TR + Sinemet:** Patients in this group will receive 36 therapy sessions targeting arm motor function starting as soon as possible after randomization (target is next day). This therapy is structured as 6 weeks of TR, 6x/week, for 6 weeks. Up to 8 weeks are permitted to make up for lost sessions to achieve 36 sessions in which >50% of assigned minutes are completed by the patient. For the first 18 sessions (approximately the first 3 weeks), the patient will take their study pill (Sinemet 25/100) 1-2 hours after breakfast or lunch, then 1 hour later begin their 70-min TR session. TR+Sinemet is in addition to UC (i.e., the patient is to continue all therapies and medication provided as part of standard medical care).
- **TR + placebo:** Patients in this group will receive 36 therapy sessions targeting arm motor function starting as soon as possible after randomization (target is next day). This therapy is structured as 6 weeks of TR, 6x/week, for 6 weeks. Up to 8 weeks are

permitted to make up for lost sessions to achieve 36 sessions in which >50% of assigned minutes are completed by the patient. For the first 18 sessions (approximately the first 3 weeks), the patient will take their study pill (placebo) 1-2 hours after breakfast or lunch, then 1 hour later begin their 70-min TR session. TR+placebo is in addition to UC (i.e., the patient is to continue all therapies and medication provided as part of standard medical care).

- **Usual care (UC):** Patients in this group will not receive TR or a blister pack of study pills. Instead, each will receive UC (i.e., will continue all therapies and medication provided as part of standard medical care). In order to maximize participant retention, patients in this group will be offered a 6-week course of TR after Visit 4 (i.e., 5-6 months after stroke). At the end of their TR therapy, at the time that their TR system is picked up from their home, the therapist will perform ARAT, FMA-UE, BBT, NHPT, and mRS in the patient's home.

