## Sample Size and Statistical Analysis

### Sample Size

The primary endpoint is the ARAT, the MCID for which is 5.7 points. This study is powered for the Aim 1 analyses, which will compare [1] patients receiving TR (i.e., combining TR+Sinemet with TR+placebo) to [2] patients receiving UC. Based on a randomization distribution of 3:3:2 (TR+Sinemet, TR+placebo, UC), and using a 2-sided alpha of 0.05, this study will have 80% power to detect a mean difference between groups of 5.7 points in the change in ARAT-time, assuming a SD of 7.4 points, with a total of 72 patients: 27 in TR+Sinemet, 27 in TR+placebo, and 18 in UC.

The study is funded to enroll 72 patients. Subject dropout may be as high as 20%, and so when possible additional patients may be enrolled.

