### Statistical Analysis

We will present descriptive statistics by group for the important covariates including age, site, time from stroke to randomization, MEP status, and hours of outside rehabilitation. We will also report compliance, defined as the percentage of the 36 sessions during which patients complete more than half ( $\geq 36$  min) of assigned activities. For all analyses, data not normally distributed will be appropriately transformed.

Primary efficacy analysis will use the Intent-To-Treat population, consisting of all randomized subjects and multiple imputation for missing data. Secondary analysis will examine the Per-Protocol population, defined as all subjects with complete data who complete  $\geq 36$  minutes of assigned activities on  $\geq 30$  of the 36 therapy sessions over no more than 8 weeks. Analyses will be performed using SAS and R software.

Logistic regression will be used to create a propensity score for treatment group using age, time from stroke to randomization, and total hours of outside rehabilitation therapy from Visit 1 to Visit 4 (or Visit 3 when change is to visit 3). Inverse weights based on this score will be used in secondary analyses to compute adjusted change distributions and corresponding p values. The primary analyses will be based on the inverse propensity score weighted (adjusted) change from base. The corresponding unadjusted changes will also be reported as a secondary analysis. Since this is a randomized trial, we expected the primary propensity adjusted and unadjusted results to be similar.

**Aim 1. TR+UC is superior to UC alone:** A 6-week program of TR targeting arm movement added to UC will result in better arm function as compared to UC alone. The primary endpoint is the change in ARAT score from baseline to 1 month after end of therapy (Visit 4).

The mean differences in ARAT score change from Visit 1 (baseline) to Visit 4 (1 month after end of therapy) will be compared on the log scale using an inverse propensity adjusted t test. A similar method will be used for the secondary change from Visit 1 to Visit 3 (end of therapy). We will first compare the combined TR + UC groups versus the UC group (Aim 1) and then compare TR+Sinemet+UC versus TR+placebo+UC under this model. (Aim 2). As a secondary analysis, we will report the corresponding unadjusted results.

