The difference in ARAT score change between [1] the combined TR group and [2] the UC group will be computed and the distributions compared using ANCOVA, adjusting for Visit 1 ARAT score and propensity score. Specifically, this Aim will compare UC vs. the combined two TR groups (TR+Sinemet plus TR+placebo).

Exploratory analyses will examine whether aphasia or neglect affect TR efficacy by determining if the extent of aphasia (Visit 1 LAST score) or neglect (Visit 1 SCT score), respectively, is correlated with change in ARAT score from Visit 1 to Visit 4. We will use a linear regression model with ARAT change as the outcome, and with treatment group, LAST score, and propensity score as predictors in order to assess the association. This will be repeated using SCT score instead of LAST score. Restricted cubic splines will be used to determine whether the relationships of language screening and neglect to ARAT score change are each linear.

An additional exploratory analysis will examine whether results vary according to the actual TR dose (the total number of arm repetitions across the 36 treatment sessions), using similar regression methods. Sex will also be explored: while females may have poorer functional outcomes after stroke, it is unclear whether the same underlying factors predict that sex will also be associated with a poorer response to rehabilitation therapy.

Analyses will be repeated examining a secondary endpoint, BBT, and then using several tertiary endpoints (FMA-UE, CES-D, mRS, NHPT, SIS-ADL, and SIS-hand). The lead secondary endpoint is the BBT, and this will be analyzed using alpha=0.05. The tertiary endpoints are considered exploratory and will be examined without correction for multiple comparisons. The same statistical methods as above will be used except that the dependent measure will be change from Visit 1 to Visit 4 in each of the secondary/tertiary endpoints. An additional analysis will examine mRS as the dependent variable but instead using a shift analysis (ordinal logistic repeated measures regression) of mRS change score from Visit 1 to Visits 3 and 4.

To aid in the interpretation of the above analyses, additional corollary analyses will repeat above but use as the dependent measure change from Visit 1 to Visit 3. This will be done for the ARAT as well as for the FMA-UE, BBT, mRS, and SIS-hand subsection.

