**Aim 2. TR+Sinemet is superior to TR+placebo:** Among patients randomized to TR, gains in arm function will be greater in those who take Sinemet (25/100) prior to daily TR, as compared to patients who take placebo prior to TR.

The above analyses will be repeated but instead comparing patients randomized to [1] TR+Sinemet vs. [2] TR+placebo.

**Aim 3. Less CST injury and higher dopamine polygene score predict better recovery of arm function:** Across all subjects, change in arm function will be highest in those with lower % CST injury and in those with higher dopamine polygene scores. These relationships will remain significant when examining only patients randomized to TR. The drug X gene score interaction term will be significant such that the slope of arm gains in relation to the polygene score will be smaller (less steep) in those receiving Sinemet.

**H3A:** Using linear regression, we will test whether lower % CST injury predicts higher change in ARAT score from Visit 1 to Visit 4, after controlling for baseline ARAT score and clinical measures (age, time from stroke to randomization, and total hours of outside rehabilitation therapy from Visit 1 to Visit 4). Primary analysis will examine all enrollees. Secondary analysis will examine this relationship separately for patients randomized to one of the two TR groups, while tertiary analysis will examine this separately across all three treatment groups.

Restricted cubic splines will be used to determine if the effect of continuous covariates such as age are linear. A linear model that includes individual clinical measures will be used rather than propensity adjustment so that the effect of % CST injury can be compared to the effects of the other covariates. This approach also allows us to test the hypothesis that % CST injury predicts ARAT gains beyond what can be learned from clinical variables alone.

**H3B:** We will test whether higher dopamine polygene score predicts higher change in ARAT score from Visit 1 to Visit 4, after controlling for the same covariates as in H3A. Analyses will follow those described in H3A.

Secondary analysis will repeat H3A and H3B using change in BBT from Visit 1 to Visit 4 as the dependent measure. Tertiary analyses will repeat these methods focusing on change in FMA-UE, CES-D, mRS, NHPT, SIS-ADL, and SIS-hand scores.

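### Aim 1 is worded as the effect of TR, but its pooled contrast takes in about half of any Sinemet effect, and no TR+placebo versus UC contrast is planned

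*Combined protocol and SAP*

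**What the plan says.** Study Aims words Aim 1 as an effect of TR itself: "A 6-week program of TR targeting arm movement added to UC will result in better arm function as compared to UC alone". The end of the Background likewise describes the goal as testing TR against an inactive control.

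The contrast is a different one. Under Statistical Analysis, Aim 1, "this Aim will compare UC vs. the combined two TR groups (TR+Sinemet plus TR+placebo". The Sample Size section is built on the same pooling, at 3:3:2 allocation (27, 27 and 18). The UC arm gets neither component: "Patients in this group will not receive TR or a blister pack of study pills".

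The group comparisons are listed in order: "We will first compare the combined TR + UC groups versus the UC group (Aim 1) and then compare TR+Sinemet+UC versus TR+placebo+UC under this model". The Aim 2 text adds only this: "The above analyses will be repeated but instead comparing patients randomized to [1] TR+Sinemet vs. [2] TR+placebo". The BBT, tertiary-endpoint, Visit 3 and Per-Protocol analyses repeat these two comparisons. The exploratory aphasia and neglect models include treatment group as a predictor but specify no TR+placebo versus UC contrast. The by-group analyses under H3A and H3B concern biomarker slopes, not differences between arms. Nothing makes the pooling depend on the Aim 2 result.

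**The concern.** The plan's two hypotheses overlap. Aim 2 expects that "gains in arm function will be greater in those who take Sinemet (25/100) prior to daily TR". If that is true, the Aim 1 difference is the TR effect plus a share of the drug effect, while the Aim 1 wording credits TR alone. A positive Aim 1 could then be reported as evidence for TR at a size, or even a significance, that TR alone would not have reached. A harmful drug effect would pull the estimate down by the same share. The arm that would separate the two, TR+placebo, is already being randomized and measured.

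**Working it through.** **Inputs.** All come from the Sample Size section: "using a 2-sided alpha of 0.05"; "80% power to detect a mean difference between groups of 5.7 points"; SD 7.4; 27 TR+Sinemet, 27 TR+placebo, 18 UC; dropout up to 20%. The drug effect D is an assumption, because the documents give none. I use 3, 4 and 5.7 points, the last being the plan's MCID.

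**1. The plan's own figure.** For 54 versus 18, SE = 7.4 × √(1/54 + 1/18) = 2.01. The noncentral t with 70 df at 5.7 points gives 79.7% power (80.8% by the normal approximation). The stated 80% reproduces.

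**2. What the pooled contrast estimates.** With equal TR arms and arm means S (TR+Sinemet), P (TR+placebo) and U (UC):

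(S + P)/2 − U = (P − U) + (S − P)/2 = (effect of TR with placebo) + D/2.

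This is exact on the raw, unweighted scale. It is approximate under inverse-propensity weighting, the log scale or unequal missingness.

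**3. Consequence when TR has no effect.** I simulated 200,000 trials per row with normal data and unadjusted two-sided t tests on raw ARAT change. The Aim 2 power column is noncentral t, 27 versus 27.

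| Assumed D | Pooled difference, D/2 | Aim 1 rejects | Aim 2 power | Aim 1 favours TR and Aim 2 not significant |
|---|---|---|---|---|
| 0 | 0 | 5% | 5% | just under 2.5% (0.025 × 0.95 ≈ 2.4%) |
| 3 | 1.5 | 11% | 31% | 7% |
| 4 | 2.0 | 15% | 50% | 8% |
| 5.7 | 2.85 | 25% | 79% | 6% |

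TR+placebo versus UC stays at 5% in every row. Inserting D/2 = 2.85 into a noncentral t with SD 7.4 would give 28.7% in the last row. That is too high, because mixing two arms whose means differ by 5.7 widens the TR group's SD to √(7.4² + 2.85²) = 7.9.

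**4. Consequence when TR has some effect.** If TR adds 2.85 and D = 5.7, the expected pooled difference is 2.85 + 2.85 = 5.7. Aim 1 then rejects in about 76% of trials, although TR alone supplies half of the difference.

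**5. The missing contrast.** For TR+placebo (27) versus UC (18), SE = 7.4 × √(1/27 + 1/18) = 2.25, so the 95% CI is about ±2.017 × 2.25 = ±4.5 points. Power for 5.7 points is 69.7%, and the difference detectable with 80% power is about 6.45 points. With 20% dropout (21.6 versus 14.4), power is 59.5%.

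**The case against.** The pooling is open. The Sample Size and Statistical Analysis sections both state it, and it is what secures 80% power with 18 UC patients. The test is valid for the question of whether a TR programme, averaged over pill type, beats UC. That stands, and it is why the pooled contrast should remain primary.

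Aim 2 estimates the drug effect on the same endpoint, directly after Aim 1. At D = 5.7 it would usually flag the drug, and the outcome that misleads (Aim 1 favours TR, Aim 2 silent) occurs in about 6% of trials. That also stands, but only in part. At D = 3, Aim 2 has 31% power, and about 70% of the trials in which Aim 1 favours TR would show a non-significant Aim 2. A non-significant Aim 2 does not show that D is zero.

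A large drug effect with no TR effect is an extreme case. The plan presents the drug as an enhancer of TR, cites a 593-patient levodopa trial that found no motor benefit (while criticising its design), and gives pills only for the first 18 sessions. This is fair. The rates above illustrate a range and are not forecasts.

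A reader might infer that Aim 1 absorbs the whole drug effect, or that a positive Aim 1 could not be attributed to TR at all. The documents support neither. At 27:27 the share is half, and the TR+placebo versus UC difference can be approximated as the pooled difference minus half the Aim 2 difference. The information is collected; what is missing is a named, pre-specified contrast with its own interval.

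**Conclusion.** The point holds as a gap between the wording of Aim 1 and its contrast. About half of any Sinemet effect enters the Aim 1 estimate, and no planned analysis shows the effect of TR without the drug. Under the assumption of no TR effect and a drug effect of 3 to 5.7 points, the pooled test rejects in about 11% to 25% of trials instead of 5%. Aim 1 favours TR without a warning from Aim 2 in about 6% to 8%, against just under 2.5% with no effects. These rates rest on assumed drug effects, normal data, SD 7.4, full enrolment without dropout and unadjusted raw-scale tests.

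They should not be read as a faulty type I error or a wrong power figure. The pooled test keeps its 5% level when neither TR nor the drug has an effect, and its 80% power is correctly computed for the combined strategy. The issue is attribution. It is worth correcting because the correction is cheap.

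**What to change.** 1. Keep the pooled contrast as the primary analysis of Aim 1.
2. Add TR+placebo versus UC as a named supportive secondary analysis of Aim 1, on the same endpoint and with the same model, reported as an estimate with 95% CI.
3. State its power: about 70% for 5.7 points at 27 versus 18, and about 59% with 20% dropout.
4. State that the pooled result will be described as the effect of TR with or without Sinemet, and interpreted alongside this contrast and Aim 2.
5. State that TR+placebo versus UC still includes any pill-expectancy effect, because UC takes no pill.

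Do not make the primary claim conditional on the two estimates being of similar size. With an interval of about ±4.5 points, such a rule would be too loose to apply unless it were defined numerically.

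The cost is one contrast and a few sentences in the analysis plan. It needs no extra patients, visits or data, and the primary power is unchanged. The drawback is the lower power of the added contrast, which is acceptable for a supportive estimate. Rewording Aim 1 alone, without the contrast, would remove the mismatch in wording but still leave no planned estimate of TR without the drug.

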Main results of the multisite, randomized, assessor-blinded trial: The 124 enrollees had baseline FMA-UE score of  $43 \pm 8$  (mean $\pm$ SD) points (maximum score, 66 points; higher scores are better), and were enrolled  $18.7 \pm 8.9$  weeks post-stroke. Compliance was 98.3% in the TR group and 93.4% in the in-clinic group. Change in FMA-UE score from baseline to 1-month post-therapy (the primary endpoint) was  $8.4 \pm 7.0$  points for the in-clinic group vs.  $7.9 \pm 6.7$  points in the TR group. The covariate-adjusted FMA-UE score change was 0.06 (95% CI -2.14, 2.26) points higher in the TR group ( $p=0.959$ ). The non-inferiority margin fell outside this 95% CI, which indicates that TR is not inferior to dose-matched therapy provided in-clinic. Motor gains associated with TR therapy remained significant whether patients were enrolled early (<90 days) or late (>90 days) post-stroke. Gains were also significant when examining change in the Box & Blocks Test (BBT) score, a measure of arm function (activities limitations). Stroke Knowledge scores also increased significantly ( $p<0.001$ ). A post hoc analysis found that TR was associated with improved global function (mRS score) in 39.5% of patients beginning therapy after day 90^14, a time when functional recovery generally stabilizes.

The number of arm movement repetitions over 36 TR treatment sessions was calculated in a convenience sample. With 70 min/day of TR, patients averaged 1,031 arm repetitions/day, 33-times higher than the amount of arm movement provided during standard of care.

Dopaminergic enhancement of rehabilitation therapy early after stroke (TR-Dopa)  
Protocol\_20230721

In sum, a 6-week course of daily home-based TR supervised by a licensed OT or PT was safe, rated favorably by subjects, associated with excellent treatment compliance, and produced substantial gains in arm function that were not inferior to a dose-matched.

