## Therapist-facing software

We developed a therapist-facing web portal that treatment therapists use for treatment planning and patient monitoring. All treatment is generated and supervised by a licensed OT or PT. Therapists use a graphical interface to drag treatment elements (functional games, exercises, and stroke education) into a 70-min planner for each day's session; they then adjust the challenge level (games) and the duration (games and exercises) of each.

**Videoconferences:** For the supervised sessions that occur for patients who are living in their home, the treatment therapist joins the patient for 60 minutes of their session using HIPAA-compliant software (VSee; Sunnyvale, CA). Supervised sessions that occur while a patient is still admitted to Cal Rehab may have the therapist join the patient via VSee or live in the patient's room, per the therapist's judgment. During supervised sessions, therapists monitor therapy and provide patients with real-time positive feedback, answer questions, perform assessments, review treatment plans, and provide encouragement. Therapists also discuss how UE movements practiced during TR can be extended to become part of activity in the home. Any AEs and serious adverse event (SAEs) are reviewed. Note that 9.7% of patients receiving TR in the national trial had shoulder pain, and all patients could be helped by their therapist remotely, without pausing TR therapy. Therapists write an electronic clinic note after each videoconference, as standard good clinical practice.

The same therapist-facing web portal allows therapists to review, at any time, from any secure location:

Usage statistics: For games and for the stroke education module, we use the TR system's sensors--every game click, tap, squeeze, or shot is sent to the lab server in real time.

Performance data: We provide therapists with concise graphic readouts of scores on each game, over time. In this way, therapists can monitor patient compliance and performance, and

then use their professional judgment to modify game/exercise choices and difficulty levels accordingly, at any time.

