## Patient-facing software

Each of the 36 TR sessions is 70 min and includes 65 min/day of functional games and exercises, plus 5 min/day of stroke education—all of which require arm movements.

(1) Arm exercises. A total of 114 UE exercises are available, each 1-5 min long and consisting of a video showing the assigned movement. Therapists may choose to demonstrate some of the exercises during videoconferences on supervised days. In addition, therapists have the option to incorporate standard exercise equipment (e.g., Theraband) that is also provided to patients at the time the TR system is delivered to the home and that can be incorporated into assigned exercises.

(2) Functional training through games. There are 25 functional games, each 1-5 min long. These stress motor control features (e.g., varying movement speed, range of motion, squeeze strength, pinch strength, target size and features, extent of visuomotor tracking, memory demand, unilateral vs. bilateral movement, or level of cognitive demand). Features are selected and adjusted by the therapist, e.g., during the whack-a-mole game, higher difficulty level means a broader area where targets can appear and less time to hit the target to score points.

Therapists also select which of the 11 input devices the patient will use for game play, based on UE motor status, e.g., vertical position of the flying bird in the flappy-bird game can be played using the grip force cylinder, pinch force cube, or trackpad. Feedback is provided during the game (e.g., when targets are hit), at the end of each game (today's score along with prior scores), and at the end of the day (graphs of progress over time).

(3) Five minutes/day of stroke education. The education content targets 5 categories (Stroke Risk Factors, Stroke Prevention, Effects of Stroke, Diet, and Exercise). During unsupervised sessions, patients answer multiple-choice questions, delivered via a video Jeopardy game format, an approach known to foster learning, and then receive feedback on their answers. Patients must make targeted arm movements to play the Stroke Jeopardy game. These 5 min/day significantly increase patient knowledge on stroke-related topics. A Stroke Knowledge Exam is administered through the TR system during the first and the last week, to measure knowledge gains in these five categories.

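### As most directly read, the exploratory TR-dose regression leaves out Visit 1 ARAT, so the dose association could be confounded by baseline severity

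*Combined protocol and SAP*

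**What the plan says.** In the Statistical Analysis section, the exploratory part of Aim 1 first asks whether aphasia or neglect is related to ARAT change from Visit 1 to Visit 4. It specifies a linear regression of ARAT change "with treatment group, LAST score, and propensity score as predictors in order to assess the association", then repeats it with the neglect score (SCT) in place of LAST. The next paragraph introduces the dose analysis, which examines "whether results vary according to the actual TR dose (the total number of arm repetitions across the 36 treatment sessions), using similar regression methods". No separate covariate list is given for it.

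The propensity score is defined earlier in the same section. It is a logistic model for treatment group on age, time from stroke to randomization, and outside rehabilitation hours. It holds no ARAT score and no other measure of severity.

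Two other models in the same section do adjust for baseline: the Aim 1 ANCOVA of ARAT change, and the H3A regression on corticospinal tract injury.

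**The concern.** Dose here means repetitions achieved, not repetitions assigned at random. It is observed after randomization, and a patient with a weaker arm may well complete fewer repetitions in the same 70 minutes. The inclusion criteria admit Visit 1 ARAT scores from 0 to 31, so ability at entry can differ widely.

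The outcome is a change score from that same baseline. It is therefore related to Visit 1 ARAT unless the Visit 4 score rises exactly one point per baseline point. If Visit 1 ARAT is related to both dose and change and is left out, part of its relation with change appears as a dose slope. That could create an apparent dose-response, hide a real one or reverse its sign.

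The result would be read with interest. The Background treats high repetition counts as the core of the therapy (a target above 800 per day). It also offers movements per session as one possible reason why the prior national trial succeeded where two in-clinic trials did not.

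**Working it through.** **Step 1. Which covariates reach the dose model?**

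| Model in Statistical Analysis | Visit 1 ARAT included? |
|---|---|
| Aim 1 ANCOVA | Yes |
| H3A linear regression | Yes |
| Aphasia/neglect regression, immediately before the dose sentence | No |
| Propensity score used in that regression | No |
| Dose regression | Not listed; described only as similar |

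The nearest antecedent is the aphasia/neglect regression. On that reading, Visit 1 ARAT enters neither directly nor through the propensity score.

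**Step 2. The plan's own figures.** The plan gives no sample size, power or effect size for the dose analysis. The number of TR patients comes from the Aim 1 calculation, which reproduces. With difference 5.7, SD 7.4, two-sided alpha 0.05, 80% power and 3:1 allocation:

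n(UC) = (1 + 1/3) × (1.960 + 0.842)² × 7.4² / 5.7² = 1.333 × 7.85 × 1.685 = 17.6, rounded up to 18.

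That gives 54 TR patients and 72 in total, as stated. Power is 80.8% by the normal formula and 79.7% by the t distribution. This step only supplies n = 54 and SD = 7.4.

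**Step 3. How large could the confounding be?** Let a = corr(baseline ARAT, dose) and b = corr(baseline ARAT, change). The documents give neither, so both are assumed. If dose has no effect at all:

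- spurious corr(dose, change) = a × b
- spurious slope per SD of dose = a × b × 7.4 ARAT points

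The rejection rates below are simulated (20,000 runs, n = 54, true dose effect zero, nominal two-sided 5%).

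| a | b | a × b | Slope (points per SD of dose) | Rejects without Visit 1 ARAT | Rejects with it |
|---|---|---|---|---|---|
| a or b = 0 | | 0 | 0 | 4.8–5.3% | 4.8–5.2% |
| 0.3 | 0.2 | 0.06 | 0.44 | 7.3% | 4.8% |
| 0.3 | 0.4 | 0.12 | 0.89 | 14.1% | 5.1% |
| 0.3 | 0.6 | 0.18 | 1.33 | 25.7% | 5.0% |
| 0.5 | 0.2 | 0.10 | 0.74 | 11.1% | 4.7% |
| 0.5 | 0.4 | 0.20 | 1.48 | 30.4% | 5.1% |
| 0.5 | 0.6 | 0.30 | 2.22 | 60.8% | 4.9% |

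Hand check of one row (a = 0.5, b = 0.4): the expected t is about 0.20 × √52 / √(1 − 0.04) = 1.47. Against a critical value of 2.007, the chance of exceeding it is about P(Z > 0.54) = 0.29, close to the simulated 30.4%.

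A negative b gives the same rejection rates with the sign of the slope reversed. The largest slope shown, 2.22 points, is 2.22 / 5.7 = 39% of the protocol's MCID per SD of dose. The simulation contains only baseline, dose and change. Pill arm, propensity score and any nonlinearity are left out.

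**The case against.** The best reply is that a similar method is not the same covariate list. The Aim 1 ANCOVA stands nearby with Visit 1 ARAT in it, and an analyst could fairly include it. The Aim 2 text also repeats the Aim 1 analyses for the two TR arms, so a TR-only model with pill arm is arguably already planned. The analysis is labelled exploratory. All of this stands. It limits the weight of the point, but the covariates are still not named and the nearest model lacks the one that matters most.

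Several stronger readings are tempting and are not supported:

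- **Exercise repetitions go uncounted.** The Therapist-facing software section says "For games and for the stroke education module, we use the TR" system's sensors, and the exercises are described as videos: "A total of 114 UE exercises are available, each 1-5 min long and consisting of a video showing the assigned movement". A reader might infer that the dose variable misses exercises. No text says so. For the prior trial the Background states: "The number of arm movement repetitions over 36 TR treatment sessions was calculated in a convenience sample". That points to a calculation whose method is not given. What can be said is that the counting method for exercises is not described.
- **Severity drives the split between games and exercises.** Patient-facing software ties the choice of input device to motor status. The game and exercise choices are left to professional judgment after review of compliance and performance.
- **A sensor-only count would shrink the slope by a known factor.** This needs invented inputs and does not always point one way. Suppose repetition rates have a CV of 15–25% and a game share uniform on 40–80% (mean 0.60). Then r² between counted and true repetitions is 0.37–0.61, and the slope per counted repetition relative to the true slope is r² divided by mean share: 0.62–1.02. With a share of 50–70%, r² is 0.70–0.86 and the ratio exceeds 1 (0.70 / 0.60 = 1.17), so the slope is inflated.
- **UC patients' zero dose biases the slope.** With treatment group in the model and every UC dose at zero, the dose slope comes from the TR patients.

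**Conclusion.** The point holds as a risk of confounding in an under-specified exploratory model. On the most direct reading, achieved dose is related to ARAT change without Visit 1 ARAT, although the plan adjusts for it in two comparable models. Under the assumed correlations, the false-positive rate for a null dose effect runs from about 5% (either correlation zero) to about 61% (0.5 and 0.6), and from 7% to 26% when the baseline-dose correlation is 0.3. Adding Visit 1 ARAT brings it to about 5% throughout. The actual size and direction cannot be given, because the documents report neither correlation.

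It would be wrong to conclude that the dose result will be confounded, or that adjustment makes it causal. Baseline ARAT does not remove confounding by adherence, fatigue or early recovery, all of which can affect both repetitions and gain. The primary Aim 1 comparison and the sample size are not affected.

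**What to change.** In Statistical Analysis, Aim 1, replace the reference to similar methods with a stated model: ARAT change from Visit 1 to Visit 4 regressed on total arm repetitions, Visit 1 ARAT, pill arm and the other covariates already intended, with the dose slope estimated among TR patients. Say that the result will be reported as an association, not as an effect of dose, and give the reason.

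Keep total repetitions as the dose measure. Completed minutes would be a debatable substitute. They are capped at 36 × 70 = 2,520, compliance in earlier TR studies was about 98% (97.9% and 98.3%), so spread may be small, and logging of minutes by activity type is not described.

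A minor clarification: state how exercise repetitions are counted. If they are not counted for every patient, label the variable as sensor-recorded game and education repetitions.

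The cost is a few lines of text and one degree of freedom. Visit 1 ARAT is already collected for eligibility, and pill arm is known from randomization.
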